STUDY TITLE:

**BIOMARKERS EVALUATION AND EFFECT OF MEPOLIZUMAB ON LOWER AND
UPPER AIRWAYS INFLAMMATION IN SEVERE REFRACTORY EOSINOPHILIC ASTHMA
AND NASAL POLYPOSIS**

NCT code:

05063981

Date last version:

12/09/2020

Type of study: Prospective Observational study

Partecipants:

PI: [name] **ICS Maugeri IRCCS Telese**
[name] and [name] **ICS Maugeri IRCCS Tradate**
[name] and [name] **ICS Mageri IRCCS Bari**
[name] **ICS Maugeri IRCCS Veruno**
[name] **CNR Pozzuoli Napoli**

Scientific rationale

Patients with severe or difficult-to-treat asthma represent a small amount of total asthmatic patients, but weight on the national health system for the costs of disease management. Chronic rhinosinusitis with nasal polyposis (CRSwNP) [1], which the Italian severe/uncontrolled asthma registry reported with a prevalence of 30% [2], represents a comorbidity that significantly impact lung function and asthma control in severe asthma [3]. Recent evidence indicates that there is a consistent heterogeneity regarding mucosal alterations present in subjects with nasal polyposis involving different pathways: inflammatory cells, remodeling, T cell activation, local IgE production, alteration induced by interactions between microorganisms and epithelial cells.

Hypothesis

Nasal, bronchial and systemic inflammation can differ among patients with severe refractory eosinophilic asthma with or without CRSwNP. Treatment with Mepolizumab could modify nasal, bronchial and systemic inflammation of patients with severe refractory eosinophilic asthma and nasal polyposis acting on disease control.

Objectives (or Research questions)

The aim of the study is to evaluate:

- differences in specific inflammatory pattern and metabolites between severe refractory asthma patients with or without nasal polyposis
- nasal, bronchial and systemic inflammation and metabolomics profile in patients with severe refractory eosinophilic asthma before and after treatment with Mepolizumab.

Study population

We will enroll 10 patients with severe refractory eosinophilic asthma plus CRSwNP and 10 patients with severe refractory eosinophilic asthma and no CRSwNP, for whom treatment with mepolizumab is indicated, according to the AIFA recommendations.

Inclusion criteria

- age >18 years
- diagnosis of severe refractory asthma according to the ERS/ATS criteria ATS

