- Blood eosinophils >150 cells/mcL at the screening visit and at least one value of 300 or more eosinophils/mcL during the previous year;
- at least two exacerbations despite maximal therapy with long-acting bronchodilators and high dose inhaled corticosteroids in the previous year or the need for continued therapy with oral corticosteroids in addition to maximal inhaled therapy for at least 6 months in the previous year
- written informed consent.
- For CRSwNP diagnosis, the EPOS 2020 guidelines will be considered as reference.

All the above-mentioned inclusion criteria must be met.

Exclusion criteria

- Pregnancy
- Eosinophilic Granulomatosis with Polyangiitis (EGPA);
- Serious life threatening cardiopulmonary disorders;
- Systemic immunologic disorder in the last 12 months;
- Positive history for malignant tumors ever in patient's life;
- Immunodeficiency.

Study design and methods

Duration of the study.

The study will last 2 years. The enrollment period will last 1 year. The follow-up period will last 1 year. Visits and collection of biological fluids will be performed at baseline and at 6 and 12 months after initiation of treatment with Mepolizumab.

The following parameters will be evaluated

- Clinical history (age of asthma onset, duration of rhinosinusitis symptoms, ASA intolerance, number of asthma exacerbations in the previous year, ACT, ACQ, Morisky Medication Adherence Scale MMAS - 8, Lund-Mackay scores, treatment, etc.);
- Snot 22;
- Nasal polyps score;
- Visual analogue scale (VAS) for main symptoms of CRSwNP
- Lung function;
- Nasal endoscopy evaluation.

Nasal inflammation. Nasal cytology: cytopsin preparations for differential cell count of eosinophils, neutrophils, macrophages, T-cells. Nasal secretions by rhinowash: ELISA tests for identification and quantitation of IL-4, IL-5, IL-3, IL-13, IF γ , eotaxin (CCL11), TSLP GMCSF.

Bronchial inflammation. In induced sputum cytopsin preparations: differential cell count of eosinophils, neutrophils, macrophages, T-cells.

In bronchial sputum supernatants by ELISA tests: IL-4, IL-5, IL-3, IL-13, IF γ , eotaxin (CCL11), TSLP GMCSF.

In cytopsin preparations some selected receptors expressed by eosinophils, neutrophils or macrophages will be analyzed after evaluation of the prevalent secreted cytokines in the supernatants.

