NMR-based metabolomics. Metabolomic analysis will be performed by NMR spectroscopy. 1D and 2D NMR spectra will be recorded at 27°C in a randomized sequential order on a 600-MHz Bruker Avance-III spectrometer equipped with a CryoProbe. Metabolites will be identified by resorting to 2D experiments and comparison with metabolite data banks.

Study Endpoints

The primary outcomes will be:

Evaluation of the differences in specific inflammatory pattern and metabolites between severe refractory asthma patients with or without nasal polyposis and correlation with clinical data.

Variation of specific inflammatory pattern and metabolites between severe asthmatic patients with or without nasal polyposis metabolites after treatment with Mepolizumab.

Statistical Plan

We will use multivariate analysis to discriminate signals/metabolites to identify hidden phenomena and trends in ensembles of NMR spectra. Subregions (buckets) of 0.02-ppm width of the spectra will be integrated using the AMIX 3.9.15 software (Bruker Biospin GmbH, Rheinstetten, Germany). Each bucket will be normalized to the total spectrum area, and the data matrix analyzed with multivariate statistical regressions. Principal Component Analysis (PCA) and Orthogonal Projection to Latent Structures Discriminant Analysis (OPLS-DA) will be carried out with the SIMCA P+14 package (Umetrics, Umeå, Sweden). PCA will first be applied to detect EBC metabolites trends and clusterings in an unsupervised (*i.e.*, no prior group knowledge is used in the calculation) manner, while OPLS-DA will be used to correlate the metabolic variations to pathophysiological changes.

We will also apply pathway topology and biomarker analysis on selected and more representative metabolites in class separation by resorting to MetaboAnalyst 4.0 software. Discriminating metabolites will be selected by evaluating both Variable Importance in Projection values greater than 1 in class discrimination and correlation values $|\rho|$ greater than 0.6.

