Data will be reported as mean \pm standard deviation or median with interquartile range. Between-group comparisons will be performed by using Analysis of Variance (cross-sectional evaluation) and Analysis of Covariance (longitudinal study) with baseline values as covariates. Depending on the distribution of variable, the use of transformations or non parametric tests will be evaluated. Categorical variables will be reported as percentage and their associations will be analysed by chi-squared or Fisher exact test as appropriate. Because of the exploratory nature of the study, sample size is not formally computed but decided a priori. A p value of <0.05 will be considered statistically significant. The statistical analyses will be carried out using professional statistical software.

Pharmacovigilance

All adverse reactions encountered during the study for both the biological drug and the concomitant drugs will be reported to local pharmacovigilance officers, as required.

Limitations

Patients will be asked to return to the clinic with a frequency not much different to that of routine disease control to reduce possible drop out.

A possible problem could be the unsuitable sputum sample or patient with too compromised lung functions to undergo sputum induction function ($FEV_1 < 1.5L$). We will collect spontaneous sputum when available, while if the patient cannot expectorate or the induced sputum collected is not suitable (sample mainly constituted by saliva), FeNO measurement will be the surrogate evaluation for eosinophilic airway inflammation.

At the co-investigator unit, a specific asthma school is present in order to properly train severe asthmatic patients to manage the disease and to reduce non adherence. This approach will be useful to avoid drop-out and loss of adherence to the protocol.

References

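### Does the baseline comparison of patients with and without nasal polyposis need an oral corticosteroid covariate?

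*Protocol*

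**What the plan says.** The Statistical Plan of the Protocol gives the models in one sentence: "Between-group comparisons will be performed by using Analysis of Variance (cross-sectional evaluation) and Analysis of Covariance (longitudinal study) with baseline values as covariates". A comparison at baseline has no earlier value to adjust for, so the covariate phrase can apply only to the longitudinal ANCOVA. For categorical data it adds: "Categorical variables will be reported as percentage and their associations will be analysed by chi-squared or Fisher exact test as appropriate". On size it says: "Because of the exploratory nature of the study, sample size is not formally computed but decided a priori".

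The groups are set under Study population: "We will enroll 10 patients with severe refractory eosinophilic asthma plus CRSwNP and 10 patients with severe refractory eosinophilic asthma and no CRSwNP". The study is observational, and no matching is stated. The Inclusion criteria offer two alternative routes on disease burden. One is at least two exacerbations in the previous year; the other is "or the need for continued therapy with oral corticosteroids in addition to maximal inhaled therapy for at least 6 months in the previous year". Treatment is recorded as part of the clinical history ("Lund-Mackay scores, treatment, etc").

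Under Study Endpoints, the first primary outcome is the difference in inflammatory pattern and metabolites "between severe refractory asthma patients with or without nasal polyposis and correlation with clinical data".

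**The concern.** Group membership follows polyp status, not randomisation, so the groups may differ in other ways. OCS use is an obvious candidate because it is one of the two entry routes, and corticosteroids could plausibly shift inflammatory markers. The Scientific rationale also says that nasal polyposis "represents a comorbidity that significantly impact lung function and asthma control in severe asthma", so unequal treatment need between the groups is conceivable.

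If one group held more OCS users and OCS changed a marker, the unadjusted ANOVA would mix the two influences. A result below 0.05 on a primary outcome could then be credited to polyposis when part of it came from treatment. Fisher's test on OCS use would seldom give warning with 10 patients per group. The natural remedy would be to tabulate OCS use by group, fit a second model with an OCS term, and call a difference robust only if both models agree.

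**Working it through.** The Protocol states no power, effect size, SD, OCS prevalence or OCS effect, so there is no stated figure to reproduce. From the documents come n = 10 + 10 and a 0.05 threshold (taken as two-sided). Every OCS figure below is an assumption.

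**1. Harm if OCS is a pure confounder.** The bias of the unadjusted difference is (prevalence in group 1 − prevalence in group 2) × OCS effect. Simulated false-positive rates, with OCS counts varying at random:

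| Assumed prevalence | Assumed OCS effect | Bias | False-positive rate |
|---|---|---|---|
| 40% vs 40% | 1 SD | 0 | 5.0% |
| 50% vs 40% | 0.5 SD | 0.10 × 0.5 = 0.05 SD | 5.0% |
| 60% vs 30% | 1 SD | 0.30 × 1 = 0.30 SD | 8.9% |
| 70% vs 30% | 1.5 SD | 0.40 × 1.5 = 0.60 SD | 18.8% |

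Holding the split fixed at 5 vs 4, 6 vs 3 and 7 vs 3 users, with the effects of the last three rows, gives about 4.4%, 6.4% and 12.9%. The harm thus runs from nothing to substantial, depending on inputs the documents do not give.

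**2. Harm from adjusting.** Suppose instead that unmeasured severity drives both OCS use and the marker, and that OCS itself has no effect on the marker. The assumed prevalences here run from 56% vs 36% to 62% vs 32%. The unadjusted difference is then unbiased, with 4.9 to 5.0% false positives. The OCS-adjusted difference is biased by 0.08 to 0.25 SD, with 5.3 to 8.3%. The ranking of the two analyses is the reverse of step 1. If severity and a 1 SD OCS effect act together, both analyses are biased: the unadjusted by 0.20 to 0.30 SD and the adjusted by 0.08 to 0.25 SD.

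**3. Cost of the OCS term.** It uses one of 18 residual degrees of freedom and multiplies the standard error of the group term by 1/√(1 − r²), where r is the correlation of OCS use with group:

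- 5 vs 3 users: r = 0.204, factor 1.02
- 6 vs 3: r = 0.302, factor 1.05
- 7 vs 3: r = 0.400, factor 1.09
- 8 vs 2: r = 0.600, factor 1.25

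This is tolerable for a sensitivity analysis, but it does not make the adjusted model the better one.

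**4. A rule that both models must agree.** Take a true difference of 1.325 SD (80% power for the ANOVA) and no OCS effect at all. Both analyses are significant in 73.8% (6 vs 3), 70.3% (7 vs 3) and 58.5% (8 vs 2) of studies. The share of ANOVA-significant results that lose the label is therefore 1 − 73.8/80 ≈ 8%, 1 − 70.3/80 ≈ 12% and 1 − 58.5/80 ≈ 27%. These would be reported as inseparable from OCS use although OCS did nothing.

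At 5 vs 5 users the two estimates are identical. An ANOVA p of 0.045 on 18 degrees of freedom corresponds to t = 2.154. If the fitted OCS coefficient is zero, t becomes 2.154 × √(17/18) = 2.094 on 17 degrees of freedom, and p = 0.052. The lost degree of freedom alone would change the label.

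**5. The question being asked.** Objectives and Study Endpoints ask for differences between patients with and without polyposis. The Hypothesis section says only that inflammation can differ between them. An unadjusted contrast estimates that difference. A claim that polyposis causes it, net of treatment, would need more, but the Protocol does not make that claim for the baseline comparison.

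**The case for a change.** The strongest case for the concern is that it takes its variable from the Protocol's own eligibility rule, leaves the ANOVA in place and costs very little. Treatment is already recorded, so a table row and a second model need little or nothing new. The existing text does not do this job: the categorical-data sentence does not name OCS, and Fisher's test has only 2.2%, 12.3% and 24.3% power for the three unequal prevalences in the table. An observed 7/10 vs 3/10 gives p = 0.18. Correlating markers with clinical data does not remove OCS from the group contrast. Even at equal underlying prevalences of 20% to 50%, the groups would differ by three or more users in 16% to 26% of studies. That does not raise the long-run false-positive rate, but readers of a 20-patient result would want to see the counts.

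The factual part stands: no covariate is attached to the baseline ANOVA, and OCS counts would help a reader. It does not follow that the document is wrong. A baseline table row and a sensitivity covariate are details that commonly sit in a statistical analysis plan. OCS is also one candidate among several recorded variables, including aspirin intolerance, exacerbations, age at onset and adherence. The entry criterion concerns OCS over the previous year, whereas an adjustment would probably use OCS at sampling.

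**Conclusion.** The concern does not hold. The Protocol fixes an unadjusted baseline comparison for a descriptive contrast in a study that calls itself exploratory, and this is neither a contradiction nor a wrong method for that question. The possible distortion, a false-positive rate between 5.0% and 18.8%, comes entirely from assumed OCS prevalences and effects. A different plausible assumption leaves the unadjusted analysis unbiased and puts a bias of 0.08 to 0.25 SD into the adjusted one. Reasonable statisticians could choose either. The one element that would change a conclusion, the requirement that both models agree, would mislabel about 8% to 27% of significant results at splits from 6 vs 3 to 8 vs 2 when OCS has no effect. What remains is a reporting preference: OCS counts by group, and perhaps an adjusted estimate beside the ANOVA. This conclusion assumes that the baseline contrast is read as a description of two groups and not as the causal effect of polyposis.

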Systemic inflammation. Blood eosinophils and neutrophil count; serum specific IgE evaluation with microarray technology; ELISA tests for IL-4, IL-5, IL-3, IL-13, IF γ , eotaxin (CCL11), TSLP GMCSF.

Metabolomic analysis in exhaled breath condensate (EBC)

Pulmonary function tests. Flow rates will be determined using automated equipment (V Max 22 System Sensor Medics, Milan, Italy) according to ATS/ERS recommendations. Static lung volumes will be determined by the helium dilution method.

Nasal cytology. Nasal cytology will be assessed with nasal brushing. Nasal blown secretions will be collected by rhino-wash and processed as previously reported and supernatants stored at -80°C for soluble mediator evaluations [4].

Induced sputum. Sputum induction will be performed using a modification of the method suggested by prof. [name]. The supernatant will be stored at -80°C for soluble markers determination by high sensitive tests ELISA

Exhaled NO. Exhaled will be measured by an electrochemical analyzer (Hypair FeNO medisoft Exp'air, 2010) according to ATS-ERS recommendations for online measurement of FeNO in adults [5] and as previously shown [6].

Inflammatory markers. Blood will be withdrawn, percentage of blood eosinophils will be determined and serum and plasma stored at -20°C for soluble biomarkers determinations. IL-4, IL-5, IL-3, IL-13, IF γ , eotaxin (CCL11), TSLP GMCSF, will be evaluated in serum or plasma, induced sputum and nasal secretion supernatants with commercially available ELISA [7] .

Furhermore the Humanitas Laboratory under direction of prof. [name] will assess the following biological markers: Innate Lymphoid Cells 2 (ILC2) in sputum, Migration Stimulating Factor (MSF) Pentatraxin 3 (PTX3) Galectin 3 (GAL3) in plasma and sputum. Interleukina-5 (IL-5) in EBC.

EBC sampling. EBC will be collected with a TURBO-DECCS condenser set at -5.0 ± 1.0 °C (Medivac, Pilastrello, Parma, Italy, Medivac.it). Briefly, all subjects will be asked to breathe at tidal volume through the mouthpiece for 15 min while sitting comfortably and wearing a nose-clip. We will obtain, on average, 2.0 ± 0.3 ml (mean \pm SD) of EBC from each subject. EBC samples will be immediately sealed in polypropylene tubes and stored first in dry ice and then at -80°C until NMR acquisition [8].

The salivary contamination of the samples will be tested by measuring their α -amylase activity.

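### Does naming FeNO as the fallback for failed sputum mix two different measurements in one analysis?

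*Protocol*

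**What the plan says.** Under Study design and methods, the bronchial assessment has two parts: "In induced sputum cytopsin preparations: differential cell count of eosinophils, neutrophils, macrophages, T-cells", and "In bronchial sputum supernatants by ELISA tests: IL-4, IL-5, IL-3, IL-13" with four further mediators. A later paragraph, under Inflammatory markers, adds "Innate Lymphoid Cells 2 (ILC2) in sputum" and three proteins measured in plasma and sputum. Exhaled NO has its own methods paragraph alongside those for lung function, nasal cytology and induced sputum. It names the analyser and the measurement standard and attaches no condition about sputum. On timing, the Protocol says "Visits and collection of biological fluids will be performed at baseline and at 6 and 12 months after initiation of treatment".

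The Limitations section foresees patients whose lung function is too poor for induction (FEV1 below 1.5 L) and samples that are unusable. The first fallback is "We will collect spontaneous sputum when available". If the patient cannot produce sputum, or the induced sample is mostly saliva, then "FeNO measurement will be the surrogate evaluation for eosinophilic airway inflammation".

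The Statistical Plan compares groups by ANOVA cross-sectionally and, over time, by "Analysis of Covariance (longitudinal study) with baseline values as covariates". Transformations or non-parametric methods may be used, depending on the distribution.

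**The concern.** The word surrogate suggests that one measurement stands in for another. A gas concentration and a cell count share no scale, and neither a transformation nor a rank test gives them one. If FeNO values filled the gaps in the sputum eosinophil variable, the ANOVA would compare mixtures. A patient with sputum at baseline and FeNO at 12 months would have no like-for-like covariate for the ANCOVA.

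The mixture might also differ between groups. Failure is linked to lung function and sputum production, and the Scientific rationale says that CRSwNP "represents a comorbidity that significantly impact lung function and asthma control in severe asthma". Sputum eosinophils belong to the inflammatory pattern in both primary outcomes, so a false or diluted difference would matter. FeNO is also missing from the list under Bronchial inflammation, which can make its status look unsettled.

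**Working it through.** The Protocol gives no failure rate, SD, effect size or power, so there is no planned figure to reproduce. The question is first one of reading, then of how much depends on assumptions.

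**1. Is a merge stated?** No. The Limitations sentence says how eosinophilic inflammation will be judged when sputum fails. Nothing there or in the Statistical Plan pools, imputes or rescales FeNO into a sputum variable.

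**2. Does the analysis text force a merge?** No. One sentence on ANOVA and ANCOVA serves every marker in nasal, bronchial and blood samples. It works only if each marker is adjusted for its own baseline. FeNO adjusted for baseline FeNO, and sputum eosinophils for baseline sputum eosinophils, both fit it.

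**3. Is FeNO only a gap-filler?** Its methods paragraph is unconditional. Absence from the Bronchial inflammation list proves little: ILC2, MSF, PTX3 and GAL3 are absent from that list too, yet are plainly planned sputum markers.

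**4. How far does the fallback reach?** Named sputum markers: 4 cell types + 8 ELISA mediators + ILC2, MSF, PTX3 and GAL3 = 16, besides receptors still to be selected. FeNO is offered for eosinophilic inflammation only, which leaves 16 - 1 = 15 without a fallback. That is no error. Those 15 have to be analysed on the samples obtained, and nothing says sputum eosinophils are treated otherwise.

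**5. What would a merge do, if someone made one?** All inputs here are assumptions.

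- *Dilution.* Let m be the share of follow-up values replaced and k the FeNO response relative to sputum, with values standardised and combined. A true -1.0 SD change reads -(1 - m) - m·k. With 70-90% adequate samples, m is 0.1-0.3. For k = 0 this gives -0.9 (m = 0.1) to -0.7 (m = 0.3); for k = 1 it is -1.0 throughout. A reading of -0.6 needs m = 0.4, that is, only 60% adequate samples.
- *Spurious difference.* With raw pooling and 10 per group, the shift in the group difference is (a - b)/10 × s, where a and b are the numbers replaced and s is the gap between the two scales. Taking s = 15 or 30 units: 4 v 1 replaced gives 0.3 × 15 = 4.5 or 0.3 × 30 = 9; 5 v 1 gives 6 or 12; equal replacement gives 0.
- *Type I error.* A simulation used 4,000 runs per scenario, a two-sided 0.05 t test, sputum mean 15 and SD 10, and FeNO SD 20. Raw pooling gave 0.07-0.09 for 4 v 1 or 1 v 4, 0.10-0.19 for 5 v 1, and 0.004-0.032 for 2 v 2 or 3 v 3. Analysed separately, the rate was 0.044-0.055 in every scenario.

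Inflation therefore needs both a merge and unequal replacement. The Protocol states neither.

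**The case for a change.** The strongest opposing case is that the surrogate rule is in the Protocol itself, so it cannot all be left to an SAP. The Protocol also never says outright that every patient has FeNO at every visit. If FeNO were taken only when sputum failed, a patient first failing at follow-up would have no baseline FeNO. Even a separate FeNO analysis would then be incomplete, and that could not be repaired later.

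The scale argument is correct: the two measures must not share a variable. The rest depends on reading the Exhaled NO paragraph as conditional, which it is not. Unequal failure is possible, but the Scientific rationale gives no size for the effect on lung function and says nothing about ability to expectorate. Low FEV1 is an obstacle to induction, with spontaneous sputum tried first.

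A separate point also stands. Patients without sputum are missing from the sputum results, which costs precision: with a two-sided t test at 0.05 and 80% power, the detectable difference is 1.32 SD with 10 per group, 1.51 with 8 and 1.63 with 7. If failure is 40% in one group and 10-20% in the other, and FEV1 correlates 0.2-0.5 with eosinophils, selection could shift the difference by 0.06-0.22 SD; with equal failure the shift is zero. This comes from missing sputum, not from naming FeNO, and keeping the markers apart does not remove it. The Protocol already lists unobtainable or unusable sputum as a limitation.

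**Conclusion.** The concern does not hold. The Protocol names FeNO as an alternative assessment where sputum is lacking, describes it as a measurement in its own right, and gives an analysis rule that fits each marker separately. The bias attributable to the plan as written is zero. The figures of -0.7 to -1.0 SD for a true -1.0 SD change, and type I error up to 0.19, arise only under an assumed merge with assumed failure rates and scales; the inflated error also needs unequal replacement between groups. An explicit statement that the two markers are analysed separately would be tidy, but that is detail an SAP commonly supplies. Its absence from the Protocol of an exploratory study of 20 patients is not an error. This conclusion rests on reading the Exhaled NO paragraph as applying to all patients, which is its plain sense.
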